10. BENEFITS

Students who participate in the intervention are likely to benefit from improved access to water in schools and increased knowledge about the importance of drinking water through improved beverage consumption patterns and improved weight status. Although the focus of this current proposal is to examine the effect of water provision and promotion on food and beverage intake patterns and obesity, there is also potential to impact health outcomes not measured in this study (e.g., dental caries).

Students at control schools will not benefit from this intervention during the study period. It is possible, however, that water dispensers given to control schools following the study could lead to improved beverage intake patterns in control schools as well. This study is beneficial to the larger population because study results can inform policies and programs that encourage children and their families to drink water instead of caloric beverages with added sugar. Subject risk is minimal, especially when compared to the potential benefits of this research.

11. PRIVACY AND CONFIDENTIALITY

All participant information and specimens are handled in compliance with the Health Insurance Portability and Accountability Act (HIPAA) and privacy policies of Stanford University, Stanford Health Care, and Stanford Children's Health.

## Statistical Analysis Plan

### Outcomes

Height and weight of students were measured by researchers using standardized protocols from the National Health and Nutrition Examination Survey study at baseline, 7-months, and 15-months. These measures were used to obtain the primary outcome of interest: prevalence of overweight and obesity in students using Centers for Disease Control and Prevention growth curves (BMI percentile for age and sex:  $\geq 85\%$  = overweight;  $\geq 95\%$  = obesity). Secondary outcomes of BMI percentile, mean BMI, BMI z-score were also obtained from these anthropometric measurements.

Other secondary outcomes included students' dietary intake. At baseline and 7-months, daily food and beverage calories were measured using a gold standard 24-hour dietary recall adapted from the National Health and Nutrition Examination Survey study that was augmented with a validated food and beverage diary method used widely in studies of school-aged children. After training on diary use led by the study team, students took home the diary (in English or Spanish), which included pictured measuring aids, measuring cups and spoons, and instructions to have an adult help with measuring and recording all beverages and foods consumed. The next day, researchers met with students individually to conduct multiple pass 24-hour recalls.

At all timepoints, a validated instrument also assessed past-week frequency of beverage consumption to examine longer-term changes in water and SSB intake.

Control variables included students' demographics including self-reported age, sex, and race and ethnicity, screen time, and physical activity. Students reported the amount of time they spent the day before the survey playing video or computer games, watching movies or programs, and doing other things on the computer or phone. Students reported the level of physical activity that made them breathe hard or sweat in the previous week as: none, sometimes (1–2 times), often (3–4 times), quite often (5–6 times), or very often (7 or more times).

### Sample Size Justification

This study is powered based upon our main outcome - percentage of overweight/obese students. For power calculations for all of our study outcomes, we assumed 80% retention of eligible students in target study classrooms at 15 months after the start of the study. Accounting for such attrition, with 26 schools, at least 50 fourth-grade students per school, and an intraclass correlation of 0.005, we had 80% power to detect a 5% between-group difference in the change in overweight prevalence at 15 months.

### Statistical Analysis

Analyses were performed in StataSE version 15.1. Mixed-effects logistic regression models examined between-group changes in the adjusted prevalence of overweight and obesity between baseline and 7- and 15-months follow-up. The primary predictor was the intervention status by

time interaction. To account for clustering, models included random intercepts for student, school, and class. Models also included random slopes that allowed for differential changes among individual students over time. We adjusted for year to capture secular trends, and controlled for students' self-reported race and ethnicity, sex, and age, and physical activity and screen time at baseline.

Similar mixed effects linear regression models assessed secondary continuous outcomes of weight status (BMI percentile, mean BMI, BMI *z*-score), dietary outcomes including total calories from foods and beverages, beverage frequency, and the proportion of students in schools observed drinking water. Because of skewed distributions, dietary outcomes were log-transformed and regression coefficients were exponentiated to derive the percent change in outcomes by intervention status over time.

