8. PARTICIPANT POPULATION

a. Planned Enrollment

1690 4th grade student participants (avg 65 per school site x 26 sites)

26 school administrators/principals (1 per school site x 26 sites)

26 food service directors/workers (1 per school site x 26 sites)

b. Age, Gender, and Ethnic Background

The age range of the participants is 7-64 years.

Gender composition: 51% male, 49% female

Ethnic background: 53% Hispanic

c. Vulnerable Populations

Children: One main aim of this study is to understand how provision and promotion of drinking water in schools affects student intake of food and beverages and child overweight/obesity. Thus, it is important to include children in this research.

Subjects unable to read, speak or understand English. Because the majority children in our study schools are Latino and may only speak Spanish, and some parents may only speak Spanish, we will not exclude Spanish-speaking populations in our study.

We will ask parents to sign an informed consent form for their child to participate in the evaluation activities. Students will also be asked to sign a written assent before participating in evaluation activities. To encourage students to complete their food and beverage diaries, they will receive a \$10-value gift card one time after completing both diaries at home with their parents. School-wide, students seen consuming water from newly installed water sources will also receive small incentives such as stickers or pencils.

d. Rationale for Exclusion of Certain Populations

We do not plan to exclude women or racial/ethnic groups from this study. Based on our previous experiences conducting research in school settings, study participants will likely be equally distributed between male and female gender. Given that one of our inclusion criteria is that schools have at least 50% of students who are eligible for free and reduced price meals (proxy for low-income households), our study population includes schools with a majority of non-White students. In our current study sample of 26 schools that have agreed to participate in the study, school populations are 66% Hispanic/Latino and 6% Black/African American.

e. Stanford Populations

None

f. Healthy Volunteers

None

g. Recruitment Details

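### The primary model is valid but leaves baseline BMI z-score unused; a 15-month logistic model adjusted for it would cut variance by roughly 12-30% at ICC 0.005

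*SAP*

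**What the plan says.** The SAP (Outcomes) makes overweight/obesity status, cut at CDC percentiles, the primary outcome. Height and weight were "measured by researchers using standardized protocols from the National Health and Nutrition Examination Survey study at baseline, 7-months, and 15-months", and the continuous scores come from the same measurements: "Secondary outcomes of BMI percentile, mean BMI, BMI z-score were also obtained from these anthropometric measurements".

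Under Statistical Analysis the primary model is set out thus: "Mixed-effects logistic regression models examined between-group changes in the adjusted prevalence of overweight and obesity". The main predictor is the interaction of arm with time. On the random part: "To account for clustering, models included random intercepts for student, school, and class"; student random slopes are added. The covariates are calendar year and students' "self-reported race and ethnicity, sex, and age, and physical activity and screen time at baseline".

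No baseline BMI, BMI percentile or BMI z-score is among the covariates. These scores are modelled only as secondary outcomes. The SAP does not say whether the model includes a separate arm difference at baseline.

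**The concern.** A contrast of changes in a yes/no status carries the binary noise of two visits. It also treats a child just under the 85th percentile at baseline exactly like a child far below it, although the first is much more likely to change category by 15 months. Baseline BMI z-score separates the two children, precedes the intervention and is already collected.

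What is at stake is the width of the confidence interval for the primary outcome in a trial of 26 schools, with power stated as 80% for a 5-point difference.

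**Working it through.** **Inputs from the documents.** The SAP (Sample Size Justification) works "with 26 schools, at least 50 fourth-grade students per school, and an intraclass correlation of 0.005". On attrition: "we assumed 80% retention of eligible students in target study classrooms at 15 months after the start of the study". It targets a 5-point difference in change with 80% power. The Protocol (sections 8a and 8i) gives 13 schools per arm and an average of 65 students per school, so 65 × 0.80 = 52 remain at 15 months.

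**Assumed, because not stated.** Two-sided alpha 0.05; prevalence p = 0.30-0.50; correlation r of BMI z-score between baseline and 15 months = 0.90-0.97; BMI z-scores bivariate normal; m = 50 per school. The scale of the ICC is not stated either, so it is varied.

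**Step 1: the plan's own figure.** With design effect 1 + 49 × 0.005 = 1.245 and 650 students per arm, 80% power for 0.05 needs SE = 0.05/2.80 = 0.0179. The inflated per-student variance must then be 650 × 0.0179²/2 ≈ 0.1035, and the variance of change V = 0.1035/1.245 ≈ 0.083. Since V = 2p(1-p)(1-φ), where φ is the within-student correlation of yes/no status, p = 0.40 requires φ ≈ 0.83. Over p = 0.30-0.50, φ is 0.80-0.83, which corresponds to r of about 0.955-0.976. So 80% is attainable for a change analysis, but cannot be confirmed from the stated inputs.

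**Step 2: closed form for the gain.** Take p = 0.40 and r = 0.95. The yes/no correlation is 0.796 at r, and 0.714 at r².

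- Change contrast: V = 2 × 0.24 × (1 - 0.796) = 0.0979.
- Adjusted for baseline z-score: A = p(1-p)[1-φ(r²)] = 0.24 × (1 - 0.714) = 0.0686.
- Adjusted for yes/no baseline only (roughly what a model with equal baselines across arms achieves): Y = p(1-p)(1-φ²) = 0.24 × (1 - 0.796²) = 0.0879.

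The cut is (comparator - A)/(comparator + S), where S is m times the school-level variance of change.

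| Reading at ICC 0.005 | S | Cut at p = 0.40, r = 0.95 | Cut over r = 0.90-0.97 |
|---|---|---|---|
| ICC describes change | 50 × 0.005 × 0.0979 = 0.0245 | 0.0293/0.1224 = 24% | about 24% |
| School-change variance is 0.005 p(1-p) | 50 × 0.005 × 0.24 = 0.0600 | 0.0293/0.1579 = 19% | 17-22% |
| Baseline held equal across arms, ICC of change | 0.0245 | 0.0193/0.1124 = 17% | 14-19% |

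The ends of the 12-30% range lie outside this table. With no school-level variance of change, the cut is 0.0293/0.0979 = 30%. If r is instead back-solved from 80% power on the 0.005 p(1-p) scale, it comes out near 0.98-0.99 and the cut is 12-15%. Prevalence hardly matters.

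With the ICC on the change scale, the first row falls to about 20% at ICC 0.01, 15% at 0.02 and 8-9% at 0.05. The third row falls to 9-11% at 0.02 and 5-6% at 0.05.

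**Step 3: simulation.** The adjusted model was logistic on arm, z and z², standardised, with school-clustered standard errors and t on 24 df.

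- Against a school-level change contrast (26 × 50, complete data, ICC 0.005), the cut was 24-26%. At r = 0.95 the SDs were 1.954 and 1.686 points, giving half-widths 2.064 × SD = 4.03 and 3.48. Rejection under the null was 4.9% for the change contrast and 4.4% for the adjusted model.
- Against a three-visit logistic model with a student random intercept (65 per school, 20% missing at 15 months), precision was measured as (mean/SD)². At r = 0.95 it was 6.84 against 8.74, a cut of 1 - 6.84/8.74 = 22%. The cut was 21% at r = 0.90 and 24% at r = 0.97. At r = 0.95 it was 15% at ICC 0.02 and 11% at ICC 0.05. With a student random slope added it was 28% (simulation interval 21-34%).
- With 20% dropout depending on 7-month status, the cut was still about 25%, with no visible bias in the arm contrast.

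**Step 4: shortcuts that fail.** Adding z-score to the three-visit model raised precision by 1.7% with complete data and 0.4% with 20% missing; both intervals include zero. A linear model of 15-month status on z-score raised the variance by about 10-12% at the r implied by 80% power.

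**The case against.** The strongest reply is that a valid, unbiased analysis matching Aim 3 is not deficient because a more efficient one exists. That stands, and it limits the point to an improvement.

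Three criticisms of the size also stand:

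- The full planned model was never simulated. The mixed-model comparator had no school or class intercepts and no covariates, and the random slope was fitted in one setting only. Its comparison sets a conditional log-odds effect against a risk difference, so it is relative standardised precision rather than a ratio of variances on one scale.
- A reader might take 21-24% as settled. It holds under one reading of the ICC, with a free arm difference at baseline. The SAP fixes neither.
- A reader might infer that the trial's primary interval would shrink from ±4.0 to ±3.5 points. Those half-widths belong to a school-level change contrast with complete data. No percentage-point width was obtained for the planned model.

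The proposal also gives something up. It covers 15 months only, drops the 7-month rows of students lost later, and needs a baseline BMI for every student, whereas the planned model keeps these records. That is a reason to keep the planned model alongside and to state missing-data rules. The SAP is in the past tense, so a labelled sensitivity analysis may be all that is possible.

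**Conclusion.** The point holds as a cheap improvement. The plan leaves precision unused on its primary outcome. Every reading examined gives a gain, roughly 12-30% of variance at ICC 0.005 and less with a larger ICC. The central figure of 24% needs the ICC of 0.005 to describe change and the baseline arm difference to be free. Prevalence, BMI z correlation and ICC scale are all assumptions.

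Two stronger conclusions might be drawn and are not supported. The planned contrast is not biased. Nor is the stated 80% power shown to be wrong, since step 1 finds it attainable. If it is right, a 21-24% cut would correspond to about 88-90% power and a 12% cut to about 85%. Those figures are conditional on the 80% and do not test it.

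**What to change.** Add to the SAP a logistic model of 15-month overweight status on arm, baseline BMI z-score (quadratic or spline) and the planned covariates. Report the standardised prevalence difference with its interval. Use school-clustered standard errors (classes lie within schools) with a small-sample correction and a t reference on about 24 df. Specify logistic explicitly, and do not substitute a linear fit or a z-score term in the planned model.

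Make it the primary 15-month analysis only if outcomes are not yet known. Otherwise report it as a labelled sensitivity analysis beside the planned model. Keep the planned model for 7 months.

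State two rules: how students without baseline BMI are handled, and how the 7-month data of dropouts are used, for example by imputing 15-month status from 7-month BMI z-score.

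The cost is a few lines of SAP text and no new data. The effect would be worded as an adjusted 15-month difference, which under randomisation has the same expectation as the difference in change.

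### The primary intervention-by-time test has no school-level term for change: if the SAP's ICC of 0.005 is an ICC of change, a nominal 5% test has a size of about 7.9%

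*SAP*

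**What the plan says.** The Protocol (8.i, Screening Procedures) plans 13 intervention and 13 control schools, and its Brief Summary calls the trial cluster randomised.

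For the primary outcome, the SAP (Statistical Analysis) specifies a mixed-effects logistic model. The test is named as follows: "The primary predictor was the intervention status by" time interaction. Two sentences set out the random part: "To account for clustering, models included random intercepts for student, school, and class", and "Models also included random slopes that allowed for differential changes among individual students over time". On trends it adds: "We adjusted for year to capture secular trends".

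The secondary outcomes follow the same pattern: "Similar mixed effects linear regression models assessed secondary continuous outcomes of weight status". The list there also covers dietary outcomes "and the proportion of students in schools observed drinking water".

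The SAP (Sample Size Justification) bases its power for a difference in change on a design "with 26 schools, at least 50 fourth-grade students per school, and an intraclass correlation of 0.005". It does not say whether that ICC describes level or change.

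Neither document states a school slope, a school-by-time effect, a cluster-robust variance or a small-sample degrees-of-freedom rule.

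**The concern.** The interaction compares change between two groups of 13 schools. A school intercept that stays constant over time adds the same amount to a student's baseline and follow-up values, so it cancels from the change. Student slopes let each child change differently but treat those changes as independent within a school. A trend that children in one school share, for example after a new cafeteria policy, therefore has no place in the interaction's standard error. That shared trend varies between the randomised units, so it is the variation against which the arm difference should be judged.

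If such variation exists, the primary confidence interval is too narrow and the test rejects a true null more often than its nominal level. The Protocol itself expects changes at school level: it surveys principals and food service directors about new policies that could affect the results (2.a, Procedures; 8.i, Screening Procedures). Those data feed exploratory analyses only.

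**Working it through.** **Inputs**
- 13 schools per arm (Protocol 8.i); at least 50 students per school, ICC 0.005 and 80% retention (SAP, Sample Size Justification).
- Average enrolment of 65 per school (Protocol 8.a). After retention, 65 × 0.8 = 52.
- Assumed, because not stated: two-sided alpha of 0.05, within-student correlation w, and correlation r of a school's effect between baseline and 15 months.

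**1. The plan's own figure.** The stated 80% power for a 5-point difference in change can be neither confirmed nor refuted, because baseline prevalence, w and alpha are not given. What it implies can be worked out. With 50 per school the design effect is 1 + 49 × 0.005 = 1.245, and the effective number per arm is 650 / 1.245 = 522. For 80% power the SD of change must be 0.05 / (2.80 × √(2/522)) = 0.288. For prevalences of 30% to 50%, SD² = 2p(1 − p)(1 − w) then gives w of about 0.80 to 0.83.

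**2. Size when the school term for change is omitted.** In the balanced linear case the true variance of the arm difference is 1 + (m − 1)ρ times the modelled one, where m is students per school and ρ is the school share of the variance in change. So:

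size = 2 × [1 − Φ(1.96 / √(1 + (m − 1)ρ))]

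| m | ρ | 1 + (m − 1)ρ | size |
|---|---|---|---|
| 50 | 0 | 1.000 | 5.0% |
| 50 | 0.0025 | 1.1225 | 6.4% |
| 50 | 0.005 | 1.245 | 7.9% |
| 40 | 0.005 | 1.195 | 7.3% |
| 52 | 0.005 | 1.255 | 8.0% |
| 65 | 0.005 | 1.320 | 8.8% |

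At m = 50 and ρ = 0.005 the true standard error is √1.245 = 1.12 times the modelled one.

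Simulated change scores (20,000 trials) gave 8.2% at that point, against 5.2% for a t test on school means with 24 df. A linear mixed model with student slopes and no school slope gave 7.6% (2,500 runs, Monte Carlo error about 0.5 points).

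**3. If 0.005 is an ICC of level.** The school variance of change is proportional to 2 × 0.005 × (1 − r) and the total variance of change to 2 × (1 − w), so ρ = 0.005 × (1 − r) / (1 − w). Taking w = 0.8, which fits step 1:
- r = 1.0: ρ = 0, size 5.0%
- r = 0.9: ρ = 0.0025, size 6.4%
- r = 0.8: ρ = 0.005, size 7.9%

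**4. Terms that might absorb part of it.**
- *Class.* An intercept for baseline class cancels just as the school intercept does. An intercept for current class need not. In a linear simulation with two reshuffled classes per school, w = 0.8 and no true class effect (all assumed), it lowered the size from 8.1% to 6.6% at ρ = 0.005 (6,184 trials, Monte Carlo error about 0.3 points).
- *Year.* A common year effect removes only a trend that schools share. If it happened to absorb half of the school variance in change, ρ would fall to 0.0025 and the size to 6.4%.

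**5. Behaviour of the remedy.** In simulated change-score trials at ρ = 0.005, a school slope fitted by maximum likelihood and tested on t(24) had a size of 4.7%, or 5.5% when a school-means test replaced it in trials with a zero variance estimate. A t test on school means held 5.0%. Maximum likelihood estimates the school variance as zero when the between-school F ratio is at most 26/24. The true variance ratio is (0.995 + 50 × 0.005) / 0.995 = 1.251, so the probability is P(F(24, 1274) ≤ 1.083 / 1.251) = 35%.

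**The case against.** The strongest reply is that the inflation is conditional. No figure in the documents shows that school trends differ, and with equal trends the planned test is valid. The same children are re-measured over 15 months, so school effects may be very stable; correlations of 0.9 to 1.0 would put the size at 6.4% to 5.0%. A current-class intercept or the year term may absorb some of the rest. The plan is also not blind to differing trends, since it surveys schools about them. All of this stands as a limit on size. None of it supplies the missing term: the surveys do not enter the primary model, and neither class nor year is stated to do this work.

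A reader might infer a type I error above 10%. The formula does give 10.8% at a change-ICC of 0.01, but that is twice the only ICC in the documents and nothing there supports it. Larger values need school effects less stable than a child's own weight status, which is not supported either.

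A reader might also extend the point to every secondary outcome. If the observed drinking proportion is analysed as one value per school and visit, school variation in change falls in its residual and that test is not inflated in this way.

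Finally, the arithmetic is linear while the primary model is logistic. A mixed logistic simulation gave 8.1% at a change-ICC of 0.0048 (2,000 trials). It omitted class, covariates and dropout, and it assumed w = 0.62, which is lower than the stated power implies, so it is only supporting evidence.

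**Conclusion.** The concern holds in conditional form. That the SAP states no school-level term for change is clear from its text. How much this matters is uncertain, because the change-ICC is not given.

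The only size anchored in a document figure is about 7.9% with 50 per school (7.3% to 8.8% for 40 to 65). It requires that 0.005 be an ICC of change, that alpha be two-sided 5%, that the linear approximation carry over, and that no other fitted term absorb school trends. Read as a level ICC, 0.005 gives 5.0% to 7.9% for school-effect correlations of 1.0 to 0.8 at a within-student correlation of 0.8. The same gap affects the student-level secondary models.

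A reader might conclude that the primary test is invalid as it stands. The documents do not support that: they show that its validity depends on an unstated assumption of equal school trends. This should be fixed, with medium confidence in its practical effect.

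**What to change.** 1. Add a school-by-time random effect or random school slope to the primary model and to the similar student-level models. The student and class terms can stay.
2. Judge the interaction on school-level degrees of freedom: 26 − 2 = 24, fewer if school-level covariates are fitted or randomisation was restricted.
3. Name one fallback for non-convergence or a zero variance estimate, which is common enough to plan for. It can be a covariate-adjusted school-level analysis of change or a permutation test over schools that respects the actual randomisation. It replaces the model in those cases and is not a second test.
4. State whether 0.005 is an ICC of level or of change, whether class means baseline or current class, and how year is coded.
5. The SAP is written in the past tense ("Analyses were performed in StataSE version 15.1"). If the analysis is already done, report the corrected analysis beside it, label it as added later, and rest the conclusion on the school-level standard error.

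No new data are needed. Intervals become somewhat wider. If the design otherwise gives 80% power (noncentrality 2.80), the t(24) reference gives about 77%, and t(20) about 76%. A school-level fallback loses the planned covariate adjustment unless it is built in, and a version based on school mean changes uses only students measured at both visits.

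### Daily food and beverage calories are tested as a difference in change between two visits; adjusting the 7-month value for baseline would be more precise, by an amount the documents do not let one fix

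*SAP*

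**What the plan says.** SAP, Outcomes, makes the calorie measures secondary and two-visit: "At baseline and 7-months, daily food and beverage calories were measured using a gold standard 24-hour dietary recall". Protocol section 2a confirms that the diaries are not repeated at 15 months. A beverage frequency questionnaire is used there instead, and it does not measure calories.

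SAP, Statistical Analysis, describes the primary logistic model first: "The primary predictor was the intervention status by" time interaction. It then lists the random terms: "To account for clustering, models included random intercepts for student, school, and class", and "Models also included random slopes that allowed for differential changes among individual students over time". The covariates are year and "self-reported race and ethnicity, sex, and age, and physical activity and screen time at baseline".

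The calorie outcomes take over this structure: "Similar mixed effects linear regression models assessed secondary continuous outcomes" of weight status and of diet. On scale and reporting, "dietary outcomes were log-transformed and regression coefficients were exponentiated to derive the percent change in outcomes by intervention status over time".

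The plan does not list the baseline calorie value as a covariate, mention a common baseline mean for the two arms, or say whether the model has an arm main effect. SAP, Sample Size Justification, gives an ICC (0.005) and power (80%) for overweight prevalence only.

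**The concern.** With two visits and a free arm effect at baseline, the interaction term subtracts the whole observed baseline difference between arms from the 7-month difference. Part of that baseline difference is noise, from day-to-day variation in intake and from the small number of schools. Subtracting all of it is efficient only if baseline and follow-up school means are almost perfectly correlated. A regression on baseline subtracts only the predictive part.

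Protocol section 1b states directional hypotheses for beverage calories (Aim 1) and food calories (Aim 2), and the SAP describes no other analysis of calories. The stake is therefore the width of the intervals on the only calorie tests of those two aims. Bias is not at issue.

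**Working it through.** The plan states no precision or power figure for calories, so there is none to reproduce. Its 80% power refers to overweight prevalence at 15 months and does not bear on this point.

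**Inputs from the documents.** 13 schools per arm (Protocol section 8i); m = 50 students per school (SAP, Sample Size Justification; the Protocol's average of 65 × 0.80 retention = 52 agrees); two visits for calories (SAP, Outcomes).

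**Inputs assumed, because the documents give none for log calories.** ICC 0.005 to 0.05 (the lower end borrows the overweight figure); student-level correlation over time within school, τ, 0.1 to 0.5; school-level correlation over time, π, 0.5 to 1; equal variance at both visits; class level ignored; complete data at first.

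**Step 1. Variances.** Let V be the variance of a school mean and r the correlation of school means between baseline and 7 months. In units of 2V/13, the variance of the arm contrast is:

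- 7-month comparison ignoring baseline: 1
- difference in change: 2(1 − r)
- baseline-adjusted at 7 months: 1 − r²

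Adjusted over change is (1 − r²) / [2(1 − r)] = (1 + r)/2, so the planned contrast loses (1 − r)/2 of its variance. It is worse than ignoring baseline when 2(1 − r) > 1, that is, when r < 0.5.

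**Step 2. From student to school level.** With D = 1 + (m − 1) × ICC,

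r = (m × ICC / D) × π + ((1 − ICC) / D) × τ.

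Example with ICC 0.005, π = 1, τ = 0.2: D = 1 + 49 × 0.005 = 1.245; r = (0.25/1.245) × 1 + (0.995/1.245) × 0.2 = 0.201 + 0.160 = 0.361; loss = (1 − 0.361)/2 = 32%.

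**Step 3. Selected results.**

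| ICC | π | τ | r | Loss (1 − r)/2 | Change variance / follow-up-only variance |
|---|---|---|---|---|---|
| 0.005 | 0.5 | 0.1 | 0.180 | 41% | 1.64 |
| 0.005 | 1.0 | 0.2 | 0.361 | 32% | 1.28 |
| 0.005 | 1.0 | 0.3 | 0.441 | 28% | 1.12 |
| 0.01 | 0.8 | 0.3 | 0.468 | 27% | 1.06 |
| 0.01 | 1.0 | 0.4 | 0.601 | 20% | 0.80 |
| 0.02 | 1.0 | 0.5 | 0.753 | 12% | 0.49 |
| 0.05 | 1.0 | 0.5 | 0.862 | 7% | 0.28 |

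The first and last rows are the extremes of the whole grid. The SAP lists no school-by-time term, which corresponds to π = 1; with π = 1 the range is 7% to 36%.

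**Step 4. Check by generalised least squares for the two-visit model.** With complete data and r = 0.36, the interaction with a free arm effect has variance 2.56, a common baseline mean gives 1.74, and follow-up only gives 2.00. The loss is 1 − 1.74/2.56 = 32%, as in the closed form. With 20% of follow-up missing, the mixed model also uses children seen once, and the saving becomes 27% (r = 0.36), 21% (r = 0.50) and 11% (r = 0.74), against 32%, 25% and 13% with complete data. The SAP's 80% retention is for 15 months; none is given for 7 months.

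**Step 5. Cost of estimating the slope.** In simulations of 4,000 trials per setting, a common baseline mean saved 33.1%, 28.3%, 20.6% and 13.3% at (ICC, overall within-child correlation) = (0.005, 0.2), (0.005, 0.3), (0.01, 0.4) and (0.02, 0.5), with a stable school effect. Regression on school-mean baseline with an estimated slope saved 29.3%, 24.7%, 16.1% and 9.2%, which is 3.6 to 4.5 points less.

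**The case against.** Four objections have weight.

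1. The model is not written out. If the arms share a baseline mean in the fitted model, nothing is lost. The calorie models also cannot copy the primary model exactly: with one value per visit at two visits, student random slopes cannot be separated from residual error. This stands as a condition on the point. An arm main effect is nonetheless the ordinary reading of an interaction model that reports change by arm.

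2. The size is assumed. A reader might infer that the plan is known to waste a particular share of variance, or that one-day intake is known to correlate weakly within a child. The documents support neither: they give no correlation or ICC for calories. Even one recall day per visit is only the natural reading, because Protocol section 8c speaks of students completing two diaries without saying when. Only the formula and a range can be claimed.

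3. A reader might infer that the planned contrast is worse than discarding baseline altogether. That holds only for r < 0.5. At r = 0.753 the change contrast has about half the variance of a follow-up-only comparison.

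4. Difference in change is valid, it concerns secondary outcomes, and it removes stable differences between arms. Students enter through parental consent, and the documents do not say whether consent came before or after school allocation. If it came after, consenting children could differ between arms, and forcing a common baseline could bias the estimate. So a reader should not infer that a free baseline difference has no value.

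The SAP is also in the past tense, so a change may come after results are known. That affects how the new analysis is labelled, not whether it is more precise.

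**Conclusion.** The point holds as one of efficiency. On the ordinary reading, the calorie contrasts for Aims 1 and 2 are differences in change, with (1 − r)/2 more of their variance than a baseline-adjusted 7-month comparison needs. Under the assumed inputs that is roughly 7% to 41% with complete data, and somewhat less with missing follow-up. In interval width, √((1 + r)/2) gives a saving of about 3% (r = 0.862: √0.931 = 0.965) to 23% (r = 0.180: √0.590 = 0.768), before the slope-estimation cost.

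The conclusion assumes an arm main effect, similar variance at both visits and equal expected baselines in the two arms. It does not show that the planned calorie results would be biased or invalid, and it does not concern the primary overweight outcome. It is worth acting on because the baseline values are already collected.

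**What to change.** State in SAP, Statistical Analysis, whether the calorie models contain an arm main effect. Then specify for food and beverage calories:

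- Model the 7-month log value on intervention, the child's baseline log value and the school-mean baseline log value, with the same covariates and with random intercepts for school and class. The student intercept and slope fall away with one outcome row per child. The school mean is needed because schools are randomised and its slope can differ from the child-level slope.
- Report the exponentiated intervention coefficient as the Aim 1 and Aim 2 calorie estimate.
- Keep the planned difference in change as a sensitivity analysis.
- A mixed model with a common baseline mean is an alternative, but not an identical one, if consent and the baseline recall both preceded knowledge of school allocation. State that timing.

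The change needs a few lines of text and no new data. Its costs are as follows. The slope is estimated from 26 schools, which gives back about four points of the variance saving. Children without a baseline recall need a stated rule. The gain relies on equal expected baselines. If calorie results have already been seen, label the adjusted analysis post hoc.
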